2.1 Anesthesia method

MAC(Monitored Anesthesia Care) monitoring anesthesia management technique.

2.2 Experimental Subjects

The patients were randomly divided into 3 groups according to the random number table method:

Remimazolam group (Group R): After intubation, remimazolam was maintained at a pump rate of 1-2 mg/kg/h until 10 minutes before the end of the operation.

Propofol group (Group P): After intubation, propofol was maintained at a pump rate of 4-10mg/kg/h until 10 minutes before the end of the operation.

Remimazolam combined with propofol group (Group C): After intubation, remimazolam at a dose of 0.3-1mg/kg/h and propofol at a dose of 3-6 mg/kg/h were maintained until 10 minutes before the end of the operation.

2.3 Preoperative Preparation

One day before the operation, the patient was visited to have a comprehensive and detailed understanding of the patient's current physiological and pathological conditions, as well as to assess the patient's cardiopulmonary function before the operation. The application of remimazolam mesylate in anesthesia was also explained to the patient. Explain the precautions for the hand surgery, and fast for 8 hours and refrain from drinking for 6 hours. Sign the informed consent form for anesthesia and the "Informed Consent Form" for the clinical trial.

2.4 Basic Preparations Before Anesthesia

2.4.1 Basic vital signs monitoring and item preparation

After the patient entered the room, their vital signs were routinely monitored using a multi-functional monitor. Including Heart rate (HR), Pulse rate (PR), Electrocardiograph (ECG), Saturation of pulse oximetry (SpO₂) Prepare emergency medicines: atropine 0.5mg, epinephrine hydrochloride 1mg, ephedrine 30mg; prepare a set of general anesthesia induction drugs: etomidate, fentanyl, cisatracurium; prepare a set of tracheal intubation tools: video laryngoscope, double-lumen bronchial catheter, sputum suction tube; Open the peripheral venous channel and fully inhale oxygen at an oxygen flow rate of 6 L/min.

2.4.2 Invasive operations

Under local anesthesia, radial artery puncture and catheterization (heparin water flushing) was selected, and invasive arterial blood pressure (IABP) was monitored.

2.5 Anesthesia induction and maintenance

After the pre-anesthesia preparations were completed, anesthesia induction began. After 3 minutes of mask inhalation of pure oxygen, the three groups were successively given fentanyl 3-5 μ g/kg, etomidate 0.4 mg/kg, and cisatracurium 0.15 mg/kg. After mask controlled oxygen inhalation for 5 minutes, after the relaxation of the mandibular muscles and anesthesia induction, a double-lumen endobronchial tube (DLT) was inserted to ensure good alignment. The anesthesia machine was adjusted to volume-controlled ventilation, and the respiratory parameters were adjusted: the tidal volume was regulated by 6-8 ml/kg and the respiratory rate was maintained to keep the end-expiratory CO₂ partial pressure at 35-45

mmHg. After the anesthesia stabilizes, a retrograde puncture and catheterization of the internal jugular vein is performed. The puncture point beside the thyroid cartilage is determined. After disinfection and laying a towel, the puncture is performed and a catheter is placed. The catheter is fixed with sutures and fluid replacement is carried out during the operation. Anesthesia maintenance: Total intravenous anesthesia was used during the operation. Intravenous anesthetics were continuously pumped according to the groups. Group R: Remimazolam was maintained at a pumping rate of 1-2mg/kg/h. Group P: Propofol was maintained at a pump speed of 4-10mg/kg/h. Group C: Maintained with remimazolam at a dose of 0.3-1mg/kg/h and propofol at a dose of 3-6 mg/kg/h. All three groups were combined with remifentanil at 6-12 μ g/kg/h, and the drug pumping speed was adjusted to maintain the BIS value at 40-60. Thirty minutes before the end of the operation, 0.15 mg/kg dezocine was administered. The infusion of remimazolam and propofol was stopped 10 minutes before the operation, and remifentanil was stopped 5 minutes before the operation.

2.6 Anesthesia Completed

After the anesthesia ended, all patients underwent lung recruitment for 30 seconds after bilateral lung ventilation was restored. The patient was sent to the PACU with a tube. After spontaneous breathing, muscle strength and consciousness were restored, sputum was suctioned and the tube was removed. The patient will be returned to the ward after assessment by the PACU physician.

3. Data collection

3.1 General Condition of the Patient

Age, gender, ASA classification, BMI, surgical method, surgical side, preoperative basic lung function

3.2 Intraoperative condition of the patient

One-lung ventilation time, blood loss, infusion volume, dosage of remimazolam, dosage of propofol, dosage of remifentanil, urine volume, blood loss, dosage of ephedrine, dosage of atropine, occurrence of hypoxemia

3.3 Cardiovascular responses of patients at all times during the perioperative period

Record the heart rate, mean arterial pressure and pulse oxygen saturation of the patient at the time of entering the room (TO), before OLV (T1), 30 minutes after OLV (T2), 60 minutes after OLV (T3), before extubation (T4), and 5 minutes after extubation (T5).

3.4 Intraoperative blood gas analysis:

All patients underwent arterial blood gas analysis and central venous blood gas analysis before OLV (T1), 30 minutes after OLV (T2), and 60 minutes after OLV (T3). Record the Pplat, VT, PEEP, OI, PaO₂, PAO₂, PcvO₂, SaO₂, ScvO₂, (A-a)DO₂, RI at these three moments, and calculate Qs/Qt and Cdyn.

3.5 Serological indicators

4mL of peripheral venous blood was collected from the patients at the time of entering the room (T0), before extubation (T4), and 24 hours after the operation (T6). The levels of serum central nervous system specific protein (S100 β) and interleukin-6 (IL-6) were detected by enzyme-linked immunosorbent assay (ELISA). Detect the white blood cell count, the percentage of neutrophils, the percentage of lymphocytes, and C-reactive protein (CRP) in the peripheral blood of the patients.

3.6 Postoperative Follow-up:

Postoperatively, Ramsay sedation scale was used to assess the recovery at 2, 4, 12 and 24 hours after surgery; VAS score was used to evaluate the pain at 2, 4, 12 and 24 hours after surgery. The number of cases requiring rescue analgesia in each group was recorded. The occurrence of postoperative adverse reactions such as restlessness, nausea and vomiting, dizziness, arrhythmia and drowsiness was recorded. The occurrence of PPCs such as pulmonary infection, respiratory failure and atelectasis within one week after surgery was recorded. The QOR-15 scale was used to assess the postoperative recovery quality at 24 and 48 hours after surgery. The postoperative hospital stay of patients was recorded.

PPCs can be diagnosed if any of the following conditions are met, in accordance with the European Perioperative Clinical Outcome (EPCO) standards jointly issued by the European Society of Anaesthesiology and the European Society of Intensive Care Medicine: (1) Pulmonary infection, suspected respiratory system infection and treated with antibiotics, and at least one of the following is met: new or changed sputum, new or progressive pulmonary infiltration shadow, fever, total white blood cell count $> 12 \times 10^9/L$. (2) Respiratory failure, $\text{PaO}_2 < 60 \text{ mmHg}$ when breathing air, $\text{PaO}_2/\text{FiO}_2 < 300 \text{ mmHg}$ or $\text{SpO}_2 < 90\%$, requiring oxygen therapy. (3) Pleural effusion confirmed by imaging. (4) Atelectasis confirmed by imaging. (5) Pneumothorax confirmed by imaging. (6) Bronchospasm, new wheezing heard and requiring treatment with bronchodilators. (7) Aspiration pneumonia: acute lung injury after aspiration of gastric contents.

IV. Statistical Analysis

Data analysis was conducted using SPSS 27.0 statistical software. Normally distributed measurement data were expressed as mean \pm standard deviation, and the comparison between groups was performed using the independent sample t-test; non-normally distributed measurement data were expressed as median and interquartile range [M(IQR)], and the comparison between groups was conducted using the Wilcoxon rank sum test. Count data were expressed as cases (%), and the comparison between groups was performed using the χ^2 test or Fisher's exact probability method. A P value < 0.05 was considered statistically significant.

The main endpoint of this study is the oxygenation index measured at 60 minutes (T3) during OLV. According to the literature, the oxygenation index of patients when they are breathing pure oxygen in both lungs and are in a state of good oxygenation is generally

between 350 and 400 mmHg. After switching to OLV, the oxygenation index drops to 150 to 200 mmHg. Therefore, any change in the oxygenation index within 50 mmHg during OLV is not clinically significant. Thus, 50 mmHg is set as the cutoff value for the disadvantage. That is, in this study, if the oxygenation index of the study group is lower than that of the control group at T4, but the difference in oxygenation indices between the two groups is within 50, then the ventilation strategy of the study group is not inferior to that of the control group in improving intraoperative oxygenation. Taking the type I error probability $\alpha = 0.025$ and the type II error probability $\beta = 0.20$, power value 0.80; using SPSS 27.0 software, the sample size for each group was calculated to be 38. Considering a 20% dropout rate and withdrawal rate, the final required sample size for each group was 50.

V. Management of Experimental Data of Subjects

1. Strictly follow the provisions of Article 1034 of the Civil Code: The personal information of natural persons is protected by law; Article 1038 stipulates: Information processors shall not disclose or tamper with the personal information they have collected and stored. Without the consent of the natural person, they shall not illegally provide the personal information to others. Protect the privacy of the subjects and prevent it from being leaked.
2. Strictly implement the provisions of Article 62 of the "Injury Liability Law": Medical institutions and their medical staff shall keep patients' privacy confidential; Article 22 of the "Physician Practice Law" stipulates: Physicians in their professional activities should care for, protect and respect patients, and safeguard their privacy.
3. The personal information of the participants is strictly confidential. The patient data will be identified by the study number rather than the patient's name. Information that can identify the patient's identity will not be disclosed to members of the research team other than the authorized personnel.
4. All research participants and the research sponsors were required to keep the patients' identities confidential. The patients' files will be stored in locked filing cabinets and can only be accessed by the researchers.
5. To ensure that the research is conducted in accordance with the regulations, when necessary, members of the government management department or the ethics committee may, as per the regulations, access the personal information of the patients at the research institution. When the research results are published, no personal information of the patients will be disclosed.

Vi. Feasibility Analysis

1. This project has obtained some preliminary research data. The scientific questions raised by the project are based on the research work that has been discovered and published. This ensures the smooth implementation of the project from both the research concept and the foundation of previous studies.

2. Regarding the hospital, the First Affiliated Hospital of Kunming Medical University is a large-scale comprehensive hospital that integrates medical treatment, teaching, research, and cadre health care. It has abundant patient resources and sufficient medications.
3. In terms of department construction, the Anesthesiology Department of the First Affiliated Hospital of Kunming Medical University is a key clinical specialty in Yunnan Province, the Anesthesia Quality Control Center of Yunnan Province, the Anesthesiology Research Center of Yunnan Province, the location of the Anesthesiology Professional Management Committee of Yunnan Hospital Management Association, a resident physician training base, and a dominant development discipline of the hospital.

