and pulmonary dynamic compliance (Cdyn) were calculated. ④ Serological indicators: 4mL of peripheral venous blood was collected from the patient immediately after the operation (T6) and 24 hours after the operation (T7). The serum central nervous system specific protein (S100 β) was detected by enzyme-linked immunosorbent assay (ELISA). Levels of interleukin-6 (IL-6) and interleukin-8 (IL-8). The white blood cell count, the percentage of neutrophils, the percentage of lymphocytes and C-reactive protein (CRP) in the peripheral blood of the patients were detected. ⑤ Postoperative recovery: The Ramsay sedation classification was used to assess the awakening status at 2, 4, 12, and 24 hours after the operation. The pain conditions at 2, 4, 12 and 24 hours after the operation were evaluated by VAS score, and the number of cases of postoperative remedial analgesia in each group of patients was recorded. Record the occurrence of postoperative adverse reactions such as restlessness, nausea and vomiting, dizziness, arrhythmia and drowsiness in each group of patients; Record the occurrence of postoperative pulmonary complications such as pulmonary infection, respiratory failure and atelectasis within one week after the operation; The postoperative recovery quality of patients was evaluated by the QOR-15 scale at 24 hours and 48 hours after the operation. Record the duration of the patient's postoperative hospital stay. Finally, the collected data will be statistically analyzed and compared.

III. Research Design

1.selective cases :

1.1 Inclusion criteria for cases:

- 1) Patients aged 65 to 75 years who are scheduled to undergo thoracoscopic surgery under general anesthesia
- 2) BMI 18~30 kg/m²;
- 3) ASA is classified into grades I to III;
- 4) There are no contraindications to the relevant drugs;
- 5) Both the patients and their families agreed to participate in this study and signed the informed consent form.

1.2 exclusion criteria:

- 6) Patients with severe sinus bradycardia (heart rate <50 beats per minute) and atrioventricular block;
- 7) Respiratory tract infection and the use of non-steroidal anti-inflammatory drugs or hormone drugs within two weeks before the operation;
- 8) People with central nervous system and mental disorders;
- 9) In the past half year, I have taken anticholinergic drugs, anticonvulsants, anti-anxiety drugs, antidepressants, etc;

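### Nine secondary outcomes have a pre-treatment (T0) value, but section IV names only unadjusted two-sample tests: valid overall, but less precise than they could be and biased when T0 differs by chance

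*Protocol*

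**What the plan says.** Section 3.3 of the protocol starts the vital-sign series at room entry: "Record the heart rate, mean arterial pressure and pulse oxygen saturation of the patient at the time of entering the room (TO" (printed with a letter O, evidently T0). It continues at T1 to T5.

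Section 3.5 has blood "collected from the patients at the time of entering the room (T0), before extubation (T4), and 24 hours after the operation (T6". It names two ELISA markers, "S100 β) and interleukin-6 (IL-6) were detected by enzyme-linked immunosorbent assay (ELISA", and four others: "Detect the white blood cell count, the percentage of neutrophils, the percentage of lymphocytes, and C-reactive protein (CRP". That makes six serum markers and three vital signs with a T0 value.

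Section 2.2 starts the allocated drug after T0. For Group R: "After intubation, remimazolam was maintained at a pump rate of 1-2 mg/kg/h until 10 minutes before the end of the operation". Groups P and C also start after intubation. T0 is therefore a pre-treatment measurement in all three groups.

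Section IV gives one general rule for continuous data: "Normally distributed measurement data were expressed as mean \pm standard deviation, and the comparison between groups was performed using the independent sample t-test", or the Wilcoxon rank sum test for non-normal data, with significance at P < 0.05. It names no covariate, change score or repeated-measures model.

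The study outline just before section III (item ④, serological indicators) gives a different serum schedule: blood "collected from the patient immediately after the operation (T6) and 24 hours after the operation (T7". It has no T0 draw, gives the label T6 a different meaning, and adds a marker: "Levels of interleukin-6 (IL-6) and interleukin-8 (IL-8".

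**The concern.** A patient who enters with high IL-6 or high arterial pressure tends to have a high value later, whatever the allocated drug. A test that ignores T0 counts that persistent difference as noise. If the arms differ at T0 by chance, part of the gap carries into the later comparison and looks like a treatment difference.

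The affected variables carry most of what sections 3.1 to 3.6 offer on haemodynamic stability, inflammation and brain injury, themes on which the background relies. The sample size was set for the oxygenation index, so precision on these outcomes was never planned for, and a covariate already being measured is worth using.

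**Working it through.** **The plan's own figures.** The protocol gives no sample size, standard deviation (SD) or correlation for these outcomes. Its only figures, 38 evaluable and 50 recruited per group, belong to the primary endpoint. No SD is stated there either, so 38 cannot be reproduced directly. With one-sided alpha 0.025, power 0.80, margin 50 mmHg and zero true difference, it implies SD = 50 / [(1.960 + 0.842) × √(2/38)] ≈ 77.8 mmHg. Dropout: 38 / 0.8 = 47.5, so 48, near the stated 50. Nothing below changes these numbers.

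**Inputs.** n = 38 or 50 per group (section IV). The 0.05 level is taken as two-sided, because sidedness is not stated. The correlation r between T0 and the later value is assumed to be 0.3, 0.5 or 0.7. T0 and later values are taken to have equal SD. The formulas are for the t-test; the rank test was not calculated.

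**Precision.** The adjusted variance is (1 − r²) times the unadjusted one. The equivalent gain in patients is 1/(1 − r²) − 1. Power for a 0.5 SD difference at 38 per group is Φ(0.5 / [√(2/38) × √(1 − r²)] − 1.96); unadjusted it is 0.59.

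| r | Variance ratio | Variance cut | Equivalent extra patients | Power |
|---|---|---|---|---|
| 0.3 | 0.91 | 9% | 10% | 0.63 |
| 0.5 | 0.75 | 25% | 33% | 0.71 |
| 0.7 | 0.51 | 49% | 96% | 0.86 |

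**Chance T0 gap.** The standard error (SE) of a T0 difference is √(2/50) = 0.20 SD at 50 per group, or √(2/38) = 0.23 SD at 38. A gap of k standard errors shifts the expected later difference by r × gap. With k = 2 at 50 per group the gap is 0.4 SD and the shift is 0.12, 0.20 or 0.28 SD. Under a true null, the chance that the unadjusted test rejects is

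1 − Φ[(1.96 − kr)/√(1 − r²)] + Φ[(−1.96 − kr)/√(1 − r²)],

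which does not depend on n once the gap is in standard errors.

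| r | k = 1 | k = 2 |
|---|---|---|
| 0.3 | 5.0% | 8.1% |
| 0.5 | 4.8% | 13.4% |
| 0.7 | 3.9% | 21.6% |

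A gap of one standard error does not inflate the rate; the problem lies with larger gaps.

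**Simulation** (20,000 two-arm trials, 38 per group, no treatment effect). Over all trials the t-test rejected in 4.9% to 5.0%. Among trials with a T0 gap at p < 0.05 it rejected in 11%, 18% and 32% for the three correlations; analysis of covariance rejected in 4% to 6%.

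**How often such gaps arise.** For one variable and one pair of groups, 5% of randomisations give a T0 gap at p < 0.05. For at least one of nine variables the chance is 1 − 0.95⁹ = 37%, if they are treated as independent, which they are not strictly.

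**Change scores.** Their variance ratio to the unadjusted comparison is 2(1 − r) = 1.4, 1.0 and 0.6. They lose precision at 0.3, break even at 0.5 and gain at 0.7. Analysis of covariance has the lower ratio at all three (0.91, 0.75, 0.51).

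**The case against.** The strongest reply is that randomisation already protects these comparisons. That stands. A reader might infer from the 8% to 22% figures that the planned tests are invalid or have an inflated error rate. They do not: those figures hold only given a T0 gap of two standard errors, and the overall rate stays at 5%.

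The benefit also rests on a correlation the documents do not give, and one range is applied to nine dissimilar variables. T0 vital signs come from awake patients, while T2 and T3 values are taken under BIS-guided anaesthesia and one-lung ventilation. SpO2 is likely to sit near its ceiling, and some markers may be driven mainly by the operation. At 0.3 or below the gain is modest. This stands as a limit on size.

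Section IV is a general rule and does not say which values are compared, so a t-test on change from T0 would also fit it. That is fair: it does not expressly exclude T0. But change scores are no more precise than the unadjusted comparison at 0.5 or below, and the named tests cannot carry a covariate. Leaving the matter to a statistical analysis plan does not resolve it, because the protocol has already named the tests and an adjusted analysis would depart from them.

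Three further readings are not supported:

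- S100β and IL-6 are not the only evidence on brain injury and inflammation, since section 3.5 also measures CRP and white-cell counts.
- The fix is not a pure wording change for the serum markers, because the outline before section III has no T0 sample.
- The primary endpoint is not involved. The oxygenation index has no T0 value, and T1 falls after the point at which the allocated infusion starts.

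**Conclusion.** The point holds as a matter of efficiency and of bias conditional on a chance T0 imbalance, for secondary outcomes only. The planned tests are valid on average. At assumed correlations of 0.3 to 0.7 they forgo a variance reduction of 9% to 49%, and they can mislead in a trial that happens to draw a large T0 gap. The gain will differ between variables and may be small for SpO2 and for surgery-driven markers. For heart rate, arterial pressure and SpO2 the conclusion rests on section 3.3 alone. For the serum markers it depends on section 3.5 being the schedule that applies. The 38 and 50 per group are unaffected. It is worth correcting, but it does not threaten the main result.

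**What to change.** State in section IV that each secondary outcome with a T0 value is compared between the three groups by analysis of covariance, or by a repeated-measures mixed model across the later time points, with the patient's own T0 value as covariate. Use a log scale, for both T0 and later values, for skewed markers such as S100β, IL-6 and CRP. Prefer this to simple change scores. Make the change before any comparison by group, so that adjustment cannot be chosen after T0 gaps are seen.

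For the vital signs this costs only analysis wording. For the serum markers, first reconcile section 3.5 (T0, T4 and T6 at 24 hours; no IL-8) with item ④ of the outline (end of operation and 24 hours only; IL-8 added), including what T6 means. The T0 covariate exists only under section 3.5. If the outline's schedule is the one in force, this adjustment is not available for the serum markers.

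### Section IV names only two-sample tests at P<0.05 for continuous outcomes, although the trial has three arms and measures most outcomes repeatedly

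*Protocol*

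**What the plan says.** Protocol section 2.2 sets up the design: "The patients were randomly divided into 3 groups according to the random number table method". These are remimazolam (R), propofol (P) and the combination (C).

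Section IV then fixes the tests by data type:
- normally distributed measurements: "the comparison between groups was performed using the independent sample t-test";
- non-normal measurements: "the comparison between groups was conducted using the Wilcoxon rank sum test";
- counts: "the comparison between groups was performed using the χ^2 test or Fisher's exact probability method".

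One threshold covers everything: "A P value < 0.05 was considered statistically significant".

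Sections 3.3 to 3.6 collect the data serially:
- heart rate, mean arterial pressure and SpO₂ at six times (T0 to T5);
- 11 recorded blood gas and ventilation variables at T1, T2 and T3, with two derived ones ("RI at these three moments, and calculate Qs/Qt and Cdyn");
- six serum or blood-count markers at T0, T4 and T6;
- Ramsay at four times, and pain likewise ("VAS score was used to evaluate the pain at 2, 4, 12 and 24 hours after surgery");
- QoR-15 at two times.

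The primary endpoint is separate: "The main endpoint of this study is the oxygenation index measured at 60 minutes (T3) during OLV". Section IV names no three-group test for continuous data, no method for repeated measurements and no multiplicity adjustment. It does not call the secondary results exploratory.

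**The concern.** The t-test and the rank-sum test each compare two groups on one value per patient. In a three-arm trial with serial outcomes, following Section IV literally means three tests at each time, each judged at 0.05. No overall test comes first, and the correlation between times is not used.

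The protocol's background section aims to show advantages of remimazolam for shunt and postoperative cognition as well as oxygenation. Apart from the primary endpoint, support for such claims would come from these secondary variables. If the regimens do not differ, the plan would still be expected to produce a number of significant pairs and times, with nothing to separate them from real effects. Several gas variables (OI, PaO₂, (A-a)DO₂, RI) draw on the same arterial sample, so one chance difference could also look like several agreeing results.

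**Working it through.** The protocol states no familywise error rate for the secondary outcomes, so there is no figure of its own to reproduce.

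**Inputs from the protocol.** Three arms give 3 pairs. The level is 0.05 per test. The planned size is 50 per arm.

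**Assumption.** The protocol gives no within-patient correlation between times, so 0.3, 0.5 and 0.7 are used.

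**Step 1: count the cells.** This uses the schedule in sections 3.3 to 3.6, continuous or scale outcomes only, leaving out T0 values and the primary (OI at T3).
- Haemodynamics: 3 × 5 = 15
- Blood gas and ventilation: 13 × 3 − 1 = 38
- Serum and blood count: 6 × 2 = 12
- Ramsay 4, VAS 4, QoR-15 2, postoperative stay 1
- Total: 15 + 38 + 12 + 4 + 4 + 2 + 1 = 76

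**Step 2: expected false positives if no arm differs.** 76 × 3 = 228 tests, and 228 × 0.05 = 11.4. This expectation does not depend on the correlations.

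**Step 3: chance of at least one P<0.05 for a single outcome.** This was simulated under no true difference, with 3 arms of 50, normal data, equal correlation between times, and all three pairwise t-tests at each time. Repeated simulations agree to about one percentage point.

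| Post-T0 times | Applies to | Correlation 0.7 down to 0.3 |
|---|---|---|
| 1 | a single-time outcome | about 12% |
| 2 | serum markers, QoR-15 | 20–23% |
| 3 | blood gas variables | 25–31% |
| 4 | VAS, Ramsay | 29–38% |
| 5 | haemodynamics | 32–45% |

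**Step 4: the whole secondary set.** This was simulated with 38 evaluable patients per arm over the 75 serial cells (25 outcomes, without postoperative stay). The chance of at least one false positive is about 0.92 to above 0.999 when correlation is low to fairly high within families of outcomes and weak across them. It falls to between 0.60 and 0.88 under very strong correlation.

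**Step 5: what drives it.** If tests were independent:
- one three-group test per cell: 1 − 0.95^75 = 0.979;
- one three-group test per outcome: 1 − 0.95^25 = 0.72.

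A three-group repeated-measures analysis therefore restores 5% within an outcome, but does not control the error across 25 outcomes.

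**The case against.** **Much of this belongs in a SAP.** Repeated-measures models and multiplicity across secondary outcomes are commonly left to that document, which is not shown. Section IV never mentions pairs or separate times, and it makes no confirmatory claim for any secondary outcome. This stands in part: pairwise, per-time testing is inferred from the tests named. But the protocol is not silent on method. It fixes two-group tests for a three-group serial design, and that is an error in the text at hand.

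**The count can be argued.**
- A reader might add the seven count outcomes (rescue analgesia, five adverse reactions, pulmonary complications). Section IV sends these to chi-square or Fisher tests, which can take three groups at once, so they do not belong.
- VT and PEEP are ventilator settings rather than drug outcomes. Dropping their 6 cells leaves 70 × 3 = 210 tests and 10.5 expected false positives.
- The study-content summary before section III gives other serum sampling times and adds IL-8, so 76 is approximate.
- If only R and C were each compared with P, the chance of at least one false positive in the whole set is 0.79 to 0.996 over the family-structured correlations examined.

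**Stronger readings that the protocol does not support.**
- A reader might infer that a false positive is nearly certain for each outcome, or that testing by pair and time is what makes it so. Steps 3 and 5 show otherwise: for one outcome it is 12–45%, and near-certainty over the set comes largely from the number of outcomes. The overlap among gas variables lowers the chance of any false positive, even though it makes one look confirmed.
- A reader might apply a six-time rate to the haemodynamics, but one of the six is the pre-drug T0 value.
- A reader might say that 5% is the error rate of nothing. It is the rate for one pair, one outcome and one time.

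**Conclusion.** The concern holds for the secondary continuous and scale outcomes. Section IV prescribes tests that do not fit the trial's own three-arm, serial design and attaches one unadjusted threshold to them. Followed literally, this raises the error for a single outcome from 5% to about 12% at one time and up to 32–45% for the haemodynamics. About 11 false positives are expected over some 228 tests if nothing differs, and at least one is very likely over the whole set.

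These figures rest on all three pairs being tested, on the schedule in sections 3.3 to 3.6, and on assumed correlations of 0.3 to 0.7 for the single-outcome rates. The primary endpoint is one outcome at one time and is outside this point. The change should be made, but it ranks below any fault that affects the primary.

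**What to change.** In Section IV, replace the two-sample tests for secondary continuous outcomes with three-group methods:

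- **Serial continuous outcomes:** one mixed model per outcome with group, time and group-by-time. Use the T0 value as a covariate where it is collected (haemodynamics, serum markers) and only post-T0 times as responses. Make one overall test of group.
- **Contrasts:** make time-averaged pairwise contrasts only if the overall test is significant. With three groups these need no further adjustment. Contrasts at individual times are not protected in this way and should be adjusted, for example by Holm.
- **Single-time outcomes:** one-way ANOVA or Kruskal-Wallis.
- **Ramsay:** a rank-based or ordinal method, since an ordinary mixed model is doubtful for this scale.
- **Status:** state that secondary outcomes are exploratory and reported as differences with 95% confidence intervals, so that the tests above support no confirmatory claim. The exception is any key secondary that the sponsor names in advance and tests after the primary. Which one to name is the sponsor's choice.

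The cost is a few sentences, with no new data or patients. The small downside is fewer nominally significant secondary results.
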